5.1 Detailed study procedures

5.1.1 Screening information

Screening information			
Step	Descriptor	Details	Appendix
1	Statement of Informed Consent	Each participate must read, understand and sign the Statement of Informed Consent before enrolled in the study. The Principal Investigator or designer conducting the informed consent discussion must sign the consent form. Note: the participate must be provided with a signed copy of this document.	
2	Demographics	Age, sex, height, weight, body mass index	
3	Healthy history	Record the participates' dietary and medical and international travel history	
4	Eligibility at screening	All responses to Inclusion Criteria questions must be answered "yes", and all responses to Exclusion Criteria questions must be answered "no" for the participate to be considered eligible	

5.1.2 Baseline period for recruiting participates.

Baseline information				
Step	Descriptor	Details	Appendix	
1	Baseline clue	Participate will complete the baseline clue measures regarding their own contact dietary habits.	exclude 9 participates	
2	BMI clue	Record participates' BMI.		
3	Measuring BMI	BMI was measured via the clinic scale.		
4	Collecting Fasting blood samples	Fasting blood samples were collected at the end of baseline for extracting amino acids	5 participates without fasting blood	

5	Collecting fecal samples	Fecal samples were self-collected and then transferred to the laboratory on dry ice and kept frozen at -80°C at baseline.	
6	Eligibility after Baseline Examination	All responses to Inclusion Criteria questions must be answered "yes", and all responses to Exclusion Criteria questions must be answered "no" for the participate to be considered eligible.	

5.1.3 Intervention period for Calorie restriction dietary intervention

Intervention information				
Step	Descriptor	Details	Appendix	
1	Prepare low-calorie meals	Common foods in low-calorie diets such as rice, vegetables, eggs, pork and beef were prepared in this study center to control experimental variables introduced by different foods and calorie estimation errors. Traditional Chinese cooking style - boiled, stir-fried and stewed, were applied for foods.		
2	Measuring BMI	BMI was measured via the clinic scale.		
3	Collecting Fasting blood samples	Fasting blood samples were collected for extracting amino acids after the intervention	5 participates without fasting blood	
4	Collecting fecal samples	Fecal samples were self-collected and then transferred to the laboratory on dry ice and kept frozen at -80°C after the intervention		
5	Eligibility after Baseline Examination	All responses to Inclusion Criteria questions must be answered "yes", and all responses to Exclusion Criteria questions must be answered "no" for the participate to be considered eligible.		

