1.4 Protocol synopsis

Protocol Number and Title: BGI-20170204 Calorie Restriction Dietary Intervention

Meals: The Normal Calorie diet at baseline and Calorie Restriction diet during Calorie Restriction period.

Phase or Type of study: Interventional

Study Objectives: The purpose of this intervention study is to evaluate the effect of calorie restriction on BMI loss, amino acid, and gut microbiota in healthy volunteers of two different enterotypes and provide useful insights for potential application of gut microbiome stratification in personalized nutrition intervention.

Study design: The study included a one-week run-in period (baseline) and a three-week CR dietary intervention period.

Sample Size: 41 individuals (24 females and 17 males aged 30 ± 6 years old) completed the whole intervention.

Eligibility Criteria:

Recruited volunteers should meet all the following criteria:

- 1) BMI less than 28 kg/m^2 and more than 18 kg/m^2 ;
- 2) Without antibiotics in the recent 2 months;
- 3) Without prebiotic or probiotic supplements in the recent 2 months;
- 4) Without hypertension, diabetes mellitus, gastrointestinal disease and other severe auto-immune diseases;
- 5) Regular eating and lifestyle patterns;
- 6) No international travel in the recent 3 months;
- 7) Without prebiotic or probiotic supplements in the recent 2 months.

Volunteers meeting any of the following criteria will not be eligible to participate in this study:

- 1) With antibiotics in the recent 2 months;
- 2) Failure to comply with the experimental requirement;

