2.2 Description of population to be studied, enrollment targets

Volunteer-wanted posters were propagated at the China National Gene Bank in Shenzhen from March to April 2017. A non-obese healthy volunteer was considered if his/her BMI less than 28 kg/m² [16]. 50 individuals met all the criteria and were recruited in this study,

and 41 individuals (24 females and 17 males aged 30 ± 6 years old) completed the whole intervention (**Table 1**). In addition, recruited volunteers should meet all the following criteria: 1) without antibiotics in the recent 2 months; 2) without prebiotic or probiotic supplements in the recent 2 months; 3) without hypertension, diabetes mellitus, gastrointestinal disease and other severe auto-immune diseases; 4) regular eating and lifestyle patterns; 5) no international travel in the recent 3 month; 6) without prebiotic or probiotic supplements in the recent 2 months. The study was approved by the institutional review board on bioethics and biosafety of BGI-Shenzhen, Shenzhen (NO. BGI-IRB 17020). All participates were fully informed of the design and purpose of this intervention study and signed a written informed consent letter.

Table 1. Cohort Description		
	Cohort	
	(Mean ± SD)	
Number of subjects	41	
Sex (female/male)	24/17	
Age	30 ± 6	
BMI (kg/m ²)	23.72 ± 2.81	
Weight(kg)	64.84± 11.57	

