#### 2.1 Sample size calculation

The primary outcome measure for the power calculation is the change of BMI between baseline and after the intervention. The sample size estimation is within the framework of Wilcoxon signed-rank test. Power analysis was conducted in G\*Power to determine a sufficient sample size using an alpha of 0.05, a power of 0.80, a medium effect size (dz = 0.5), and two tails [4]. Based on the aforementioned assumptions, the desired sample size is 35. We have conservatively assumed that the overall dropout rate will be 30% during the 4-week study period. To account for loss to follow-up, the power will be 80% if 50 study subjects are recruited.

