# 5. Populations to be analyzed

41 participates will be analyzed in this study.

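### As written, the protocol repeats the eligibility check after the post-intervention measurements, and the SAP defines its population only as a count of 41, so it is unclear whether everyone who started calorie restriction is analysed

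*Protocol*

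**What the plan says.** **Eligibility.** The baseline table (Protocol 5.1.2) ends with an eligibility check at step 6. The intervention table (5.1.3) ends with the same check, word for word, at step 5, after BMI, blood and stool have been collected: "all responses to Exclusion Criteria questions must be answered" no, and all inclusion questions yes. The title of step 5 still refers to the baseline examination.

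**Criteria.** The Protocol synopsis (1.4) requires BMI above 18 and below 28 kg/m². Its second exclusion criterion is "Failure to comply with the experimental requirement", with no definition, threshold or time point.

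**Numbers.** Protocol 2.2 states that "50 individuals met all the criteria and were recruited in this study" and that 41 completed; SAP 2 agrees. The baseline table carries the note "exclude 9 participates" against step 1, the dietary-habits step. The Figure 1 legend in both documents calls the 41 enrolled. SAP 5 reads, in full, "41 participates will be analyzed in this study".

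**Outcome and missing data.** Protocol 4.1 takes post-intervention BMI as the average of measurements in the last CR week. SAP 2.1 allows for 30% dropout over the four weeks. SAP 7 covers missing amino acids only.

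**The concern.** An eligibility check made after the outcome has been measured can select on behaviour or response during treatment. Two criteria allow this. Failure to comply may be judged on conduct during the diet, and a lean participant can fall below BMI 18 because the diet worked. SAP 5 would not prevent such removals, because it names a count and not a rule for who belongs in the set.

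The documents also do not say how many people started CR. If some of the 9 left during it, the first primary outcome (mean BMI change) would describe completers and might be overstated. The second (the difference between 28 Bacteroides and 13 Prevotella participants) could be distorted if tolerance of the diet differed by enterotype. Someone who stopped before the last week has no primary outcome value under Protocol 4.1, and no rule in the SAP covers that case.

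**Working it through.** **1. The plan's own sample size.** Inputs (SAP 2.1): "using an alpha of 0.05, a power of 0.80, a medium effect size (dz = 0.5), and two tails"; "The sample size estimation is within the framework of Wilcoxon signed-rank test". The check uses noncentral t power with n multiplied by the asymptotic relative efficiency 3/π (normal data). At n = 35 the power is 0.801, and simulation also gives 0.801. So "the desired sample size is 35" reproduces. Dropout: 35/(1 − 0.30) = 50, which also reproduces. With 41 analysed, power is about 0.86. The loss of 9 is therefore not a power problem; the question is selection.

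**2. When did the 9 leave?**

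| Place | What it says | What it implies |
|---|---|---|
| Protocol 5.1.2, step 1 | 9 excluded, noted in the baseline table | Left before CR; 50 − 9 = 41 |
| Protocol 5.1.3 | Only note: 5 without fasting blood | No exclusion recorded during CR |
| Figure 1 legend, both documents | 41 enrolled | Fits departure before CR |
| Protocol 2.2, SAP 2 | 50 eligible and recruited, 41 completed | Fits either timing; reads as attrition |
| SAP 2.1 | 30% dropout over four weeks | Planning assumption that includes the run-in; settles nothing |

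Share of CR starters not analysed: 0/41 = 0% if all 9 left at baseline, and 9/50 = 18% if all 9 left during CR.

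**3. Bound on mean BMI change.** Assume all 9 started CR and their mean change was f times the completer mean. The mean over starters, as a fraction of the completer mean, is (41 + 9f)/50. The documents give no value for f, so a range is shown:
- f = 0.5: 45.5/50 = 0.91
- f = 0: 41/50 = 0.82
- f = −0.5: 36.5/50 = 0.73

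**4. Bound on the enterotype contrast.** Assume f = 0 and that completers of both enterotypes lose the same amount d. Completer counts (28 and 13) are from Protocol 4.1; the split of the 9 is assumed.

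| Split of the 9 (Bacteroides/Prevotella) | Bacteroides starters | Prevotella starters | Gap |
|---|---|---|---|
| 6/3 (near proportional) | 28/34 = 0.82d | 13/16 = 0.81d | 0.01d |
| 0/9 | 28/28 = 1.00d | 13/22 = 0.59d | 0.41d |
| 9/0 | 28/37 = 0.76d | 13/13 = 1.00d | 0.24d |

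**5. The BMI floor.** Inputs: baseline BMI 23.72 ± 2.81 in 41 people (Table 1), normality assumed. Entry already requires BMI above 18, so the people at risk lie between 18 and 18 plus the loss. For an assumed loss of 1 kg/m²: 41 × [Φ((19 − 23.72)/2.81) − Φ((18 − 23.72)/2.81)] = 41 × (0.0465 − 0.0209) = 1.05. The loss is an assumption; with 0.5 kg/m² the expected number is 41 × (0.0316 − 0.0209) = 0.4, and with 2 kg/m² it is 41 × (0.0928 − 0.0209) = 2.9.

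**The case against.** A reader might infer that the primary result is known to describe compliant completers and not those who started the diet. The documents do not support that.

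- **Timing.** The only place that ties the 9 to a stage is the baseline table, and 50 − 9 gives exactly the 41 analysed. On that reading the analysis includes every starter. Recruiting 50 and then excluding 9 is compatible with the separate checks at screening and after baseline.
- **The repeated step.** Its title points to baseline and its text duplicates the baseline row, so it is probably a copying error. Nothing says that anyone was removed, or any data dropped, under it.
- **Compliance.** No reason is given for any of the 9. The criterion could also be judged in the run-in, when volunteers were given dietary advice (Protocol 2.3).
- **Direction.** Removing non-compliers would tend to raise the mean loss, but removing people who fell below BMI 18 would tend to lower it. An unconditional claim of inflation fails.
- **Enterotype.** The large gaps need all 9 losses to fall in one group; a near-proportional split leaves almost none.

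All of this stands, and it limits the point to a possible bias. It does not remove the defect in the text: the check is listed after the outcome measurements, the compliance criterion has no time point, the SAP population is only a count, and neither document states the number who started CR.

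**Conclusion.** The point holds as a defect in the stated rules and in the definition of the analysis population; bias in the result is not shown. If all 9 left before CR, which the baseline table favours, the set of 41 is right and the bias from this source is zero. If all 9 started CR and did not change, the mean over starters is 82% of the completer mean (73% to 91% over the range tried). The enterotype gap then runs from 0.01d with a near-proportional split to 0.41d if every loss was Prevotella. The BMI floor concerns about 1 of 41 people, assuming normality and a loss of about 1 kg/m². Confidence is high that the step as written and the undefined population need correction, and moderate at most that the result is actually biased.

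**What to change.** 1. **Protocol 5.1.3 and 1.4.** Delete step 5 of the intervention table, so that eligibility ends at step 6 of 5.1.2. State what the compliance criterion means and when it applies. Record non-compliance after CR starts as adherence, not as a reason for exclusion from analysis.
2. **SAP 5 and 7.** Define the primary BMI population as everyone who started CR, with completers as a secondary set. If any starter lacks a post-intervention BMI, add a sensitivity analysis, for example with the change set to zero or with the last on-diet BMI where one was recorded.
3. **Participant flow.** Reconcile Protocol 2.2, Protocol 5.1.2, SAP 2 and the Figure 1 legend: state how many started CR, and when and why the 9 left, by enterotype where a baseline stool sample exists. If all 9 left before CR, say so; the set of 41 then stands and no sensitivity analysis is needed on their account.

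The cost is a few wording changes, a flow statement and at most one extra table. On-diet BMI may not exist for people who stopped early, because Protocol 4.1 describes repeated measurement only in the last CR week; the zero-change analysis does not need it. The reported mean BMI loss may become somewhat smaller.

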6.1 Statistical methods to be employed

All outcomes will be presented using descriptive statistics: Wilcoxon rank-sum test is used to detect the significant differences on phenotypes, the concentrations of blood amino acids and the relative abundances of genera and species between enterotypes. Wilcoxon signedrank test is used to detect the significant differences on phenotypes, the concentrations of blood amino acids and the relative abundances of genera and species in paired samples before and after the intervention. Permutational multivariate analysis of variance (PERMANOVA) is used to detect the association between enterotypes and the overall blood amino acid profile at baseline by using PERMANOVA with 9,999 permutations on enterotypes. Principal coordinate analysis is used to visual overall gut microbial based on the relative abundance profiles between baseline and after the intervention. Principal component analysis is used to visual overall amino acid composition based on the blood amino acid profiles between baseline and after the intervention. To investigate whether we could predict BMI loss ratio using omics features, we will perform a Lasso (Least absolute shrinkage and selection operator) regression analysis between baseline relative abundances of gut common species and the concentrations of blood amino acids (independent variables), and BMI loss ratio (dependent variables). We first normalize values of both independent and dependent variables (R, scale function). We then use the R function cv.glmnet to choose the most appropriate value for λ in the Lasso model (R glmnet package, alpha =1, family="gaussian", nfolds=10, alpha=1, nlambda=100). Here, λ is the tuning parameter ($\lambda > 0$) which controls the strength of the shrinkage of the variables. We then apply the Lasso feature selection process by shrinking the Lasso regression coefficients of non-informative variables to zero and selecting the variables of non-zero coefficients. To reduce overfitting with a limited sample size (n=41), we apply leave-one-out cross validation (LOOCV) to estimate the prediction performance of BMI loss ratio using a generalized linear model (GLM) of the selected features (creatFolds function in R caret package and the glm function in R base package). Likewise, we also use baseline BMI values for LOOCV to estimate its prediction performance for CR-associated BMI loss ratio. Spearman's rho values will be calculated between actual BMI loss ratios and the predicted values. P-value adjustment is applied for multiple hypothesis testing on the concentrations

# Abbreviations

CR	Calorie restriction
BMI	Body mass index
ETB	Enterotype Bacteroides
ETP	Enterotype Prevotella
BH	Benjamini-Hochberg
LC-MS/MS	Liquid chromatography-mass spectrometry
Lasso	Least absolute shrinkage and selection operator
LOOCV	leave-one-out cross validation
GLM	generalized linear model
PERMANOVA	Permutational multivariate analysis of variance

## 1. Introduction

The aim of this project is to simultaneously evaluate impacts of CR on BMI, gut microbiota and blood amino acids in nonobese individuals.

This statistical analysis plan (SAP) will give more detailed description of the endpoints in the study and the corresponding analyses

## 2. Study design

Volunteer-wanted posters were propagated at the China National Gene Bank in Shenzhen from March to April 2017. A non-obese healthy volunteer was considered if his/her BMI less than 28 kg/m^2.[1] In addition, recruited volunteers should meet all the following criteria: 1) without antibiotics in the recent 2 months; 2) without prebiotic or probiotic supplements in the recent 2 months; 3) without hypertension, diabetes mellitus, gastrointestinal disease and other severe auto-immune disease; 4) regular eating and lifestyle patterns; 5) no international travel in the recent 3 month; 6) without prebiotic or probiotic or probiotic supplements in the recent 2 months. 50 individuals met all the criteria and were recruited in this study, and 41 individuals (24 females and 17 males aged  $30 \pm 6$  years old) completed the whole intervention (**Table 1**).

Table 1. Cohort Description		
	Cohort	
	(Mean ± SD)	
Number of subjects	41	
Sex (female/male)	24/17	
Age	$30 \pm 6$	
BMI (kg/m  )	$23.72 \pm 2.81$	
Weight(kg)	$64.84 \pm 11.57$	

The study included a one-week run-in period (baseline) and a three-week CR dietary intervention period.

During the first week (run-in period), all healthy volunteers consumed their usual diet and were encouraged to avoid yogurt, high-fat foods and alcohol. The CR diet was comprised of ~50% calories of a normal-calorie diet (female, 1000kcal/day; male, 1200kcal/day). It was designed with carbohydrate, fat and protein as approximately 55%, 30% and 15% of the total energy intake respectively, according to the Dietary Guidelines for Chinese Residents (2016) and nutritionally balanced [2] and a recent large nutritional study in China [3]. Common foods in low-calorie diets such as rice, vegetables, eggs, pork and beef were prepared in this study center to control experimental variables introduced by different foods and calorie estimation errors. Traditional Chinese cooking style - boiled, stir-fried and stewed, were applied for foods. For each meal, digital scales were used to measure the nutritional and caloric values of different foods and total meal for male and female respectively. BMI, blood and fecal samples of each volunteer were collected at this study center at baseline and after the 3-week CR intervention (**Figure 1**).

Figure 1 Overview of the experimental design. Illustration of experimental design, including a 1-week runin period (baseline) and a 3-week calorie restriction (CR) dietary intervention trial with 50% energy deficit diet (male, ~1200Kcal/day; female, ~1000Kcal/day). BMI, fasting blood samples and fecal samples of 41 enrolled healthy subjects were collected before and after the CR intervention to assess its effects on BMI, blood amino acids and gut microbiome in two enterotype groups.

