2.1 Background

Calorie restriction (CR), which has the potential effect on weight loss and blood amino acids, has been demonstrated to associate with gut microbiota in human, especially in obese individuals [1, 2]. Observational studies with long-term CR found that CR resulted in weight loss and decreasing chronic disease risk factors in nonobese persons [3-6]. A 4week CR intervention improved gut barrier integrity, reduced systemic inflammation on gut microbial diversity and BMI loss in obese women, suggesting a potential association among gut microbiota, CR and BMI [7]. Enterotype, a concept for stratifying individuals based on the gut microbiota, was first described in 2011 and was closely linked to longterm dietary patterns [8, 9]. Plenty of studies have reported that individuals have shown microbial-dependent (enterotypes, *Bacteroides* to *Prevotella* ratio) metabolic responses to the same intervention, including changes of BMI and glycemic indices [9-14]. As for the association between CR and blood amino acids, Biolo et.al reported changes in blood amino acids of 9 healthy nonobese men after a 2-week CR diet [15]. Despite the plenty of studies on CR as we mentioned above, to our knowledge, there are no studies for simultaneously evaluating impacts of CR on BMI, gut microbiota and blood amino acids in nonobese individuals in a single study.

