4.1 Primary and secondary outcomes

The primary outcomes for this study are:

- Change in BMI of all volunteers (n=41) following calorie restriction dietary intervention
- Different changes in BMI between enterotypes *Bacteroides* (n=28) and enterotypes *Prevotella* (n=13) following calorie restriction dietary intervention

BMI was measured via the clinic scale. To avoid intra-individual variations, BMI was collected multiple times of each volunteer during the last week of the CR intervention, and the averaged BMI value was used as his/her after-intervention BMI.

The secondary outcomes for this study are:

- Change in the concentration of 31 blood amino acids of 36 volunteers following calorie restriction dietary intervention
- Different in the concentration of 31 blood amino acids between enterotypes *Bacteroides* (n=25) and enterotypes *Prevotella* (n=11) following calorie restriction dietary intervention
- Change in the gut microbiota of all the volunteers (n=41) following calorie restriction dietary intervention
- Different in the gut microbiota of between enterotypes *Bacteroides* (n=28) and enterotypes *Prevotella* (n=13) following calorie restriction dietary intervention

The concentrations of 31 amino acids and derivatives in the fasting serum samples were measured by LC-MS/MS. Fasting blood samples were collected before and after the

intervention for amino acid analysis. These blood samples were then centrifuged, and serum samples were collected and stored at -80 °C. The concentrations of 31 amino acids and derivatives in the serum samples were then measured via ultra-high pressure liquid chromatography (UHPLC) coupled to an AB Sciex Qtrap 5500 mass spectrometry (AB Sciex, US) as described previously [19].

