#### 6. Analyses

All outcomes will be presented using descriptive statistics: Wilcoxon rank-sum test is used to detect the significant differences on phenotypes, the concentrations of blood amino acids and the relative abundances of genera and species between enterotypes. Wilcoxon signedrank test is used to detect the significant differences on phenotypes, the concentrations of blood amino acids and the relative abundances of genera and species in paired samples before and after the intervention. Permutational multivariate analysis of variance (PERMANOVA) is used to detect the association between enterotypes and the overall blood amino acid profile at baseline by using PERMANOVA with 9,999 permutations on enterotypes. Principal coordinate analysis is used to visual overall gut microbial based on the relative abundance profiles between baseline and after the intervention. Principal component analysis is used to visual overall amino acid composition based on the blood amino acid profiles between baseline and after the intervention. To investigate whether we could predict BMI loss ratio using omics features, we will perform a Lasso (Least absolute shrinkage and selection operator) regression analysis between baseline relative abundances of gut common species and the concentrations of blood amino acids (independent variables), and BMI loss ratio (dependent variables). We first normalize values of both independent and dependent variables (R, scale function). We then use the R function cv.glmnet to choose the most appropriate value for  $\lambda$  in the Lasso model (R glmnet package, alpha =1, family="gaussian", nfolds=10, alpha=1, nlambda=100). Here,  $\lambda$  is the tuning parameter ( $\lambda > 0$ ) which controls the strength of the shrinkage of the variables. We then apply the Lasso feature selection process by shrinking the Lasso regression coefficients of non-informative variables to zero and selecting the variables of non-zero coefficients. To reduce overfitting with a limited sample size (n=41), we apply leave-one-out cross

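### If enterotype is assigned from baseline Prevotella and Bacteroides, by-enterotype change in those same taxa can be regression to the mean, and the SAP does not guard against it

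*SAP*

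**What the plan says.** **Aim.** The Figure 1 legend (SAP section 2) gives the purpose of the paired sampling as "to assess its effects on BMI, blood amino acids and gut microbiome in two enterotype groups". SAP section 3 and Protocol 3.1 also frame the diet effect in terms of two enterotypes. Protocol 4.1 lists as a secondary outcome "Different in the gut microbiota of between enterotypes" Bacteroides (28 people) and Prevotella (13 people) after the diet.

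**Tests.** SAP section 6 applies the signed-rank test to "the relative abundances of genera and species in paired samples before and after the intervention" and the rank-sum test to "the relative abundances of genera and species between enterotypes". Neither test excludes the two genera that name the groups. Benjamini-Hochberg adjustment is planned for genera and species.

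**Enterotype.** Protocol 2.1 describes it as "Enterotype, a concept for stratifying individuals based on the gut microbiota", and reports that "individuals have shown microbial-dependent (enterotypes, *Bacteroides* to *Prevotella* ratio) metabolic responses" occur. SAP section 6 uses the label to examine "the association between enterotypes and the overall blood amino acid profile at baseline". No assignment rule, list of taxa or classifying sample is given.

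**Design.** Stool is described at two times only, baseline and after three weeks of the diet. Everyone receives the diet.

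**The concern.** A single stool sample measures a person's usual abundance with error. If that sample also decides the group, people whose Prevotella was high by chance that day tend to fall in the Prevotella group, and people whose Prevotella was low by chance tend to fall in the Bacteroides group. At the second sample the chance part is drawn afresh. Prevotella then falls on average in the first group and rises in the second, even if the diet does nothing.

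This is a bias in change over time. It is separate from the obvious fact that levels of these genera differ between groups by construction, and analysing change scores instead of levels does not remove it.

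At stake is the interpretation of the genera that readers will look at first. A fall in Prevotella confined to the Prevotella group would be read as an enterotype-specific diet response, which is close to the study's stated purpose.

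**Working it through.** **The plan's own figure.** The only stated calculation is the sample size for BMI change (SAP 2.1). It reproduces: with dz = 0.5, two-sided alpha 0.05 and the Wilcoxon efficiency 3/π, 35 people give power 0.801, and 35/(1 − 0.30) = 50. It has no bearing on the taxa, so the check below is a simulation.

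**Inputs from the documents.** 41 people in groups of 13 and 28; one sample before and one after; rank-sum and signed-rank tests.

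**Assumptions.** The documents give neither the reliability of a single stool sample nor the separation of the enterotypes. Reliability r is varied from 0.6 to 0.9 in the main table. True levels follow either one normal distribution (a continuous gradient) or a 28/13 mixture whose separation is counted in within-cluster SDs of the true level. There is no diet effect. The 13 highest baseline scores are labelled Prevotella.

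**Direction and size of the drift (continuous gradient).** Expected change in a group = −(1 − r) × the group's mean baseline deviation. At r = 0.5 the simulated change in the 13 is −0.549 SD, so their mean deviation is 0.549/0.5 = 1.10 SD. The formula then gives:

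- r = 0.8: −0.2 × 1.10 = −0.22 SD (simulated −0.225; the 28 rise by 0.108)
- r = 0.9: −0.1 × 1.10 = −0.11 SD (simulated −0.111; the 28 rise by 0.053)

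The two drifts cancel in the whole cohort. At r = 0.8, [13 × (−0.225) + 28 × 0.108]/41 = 0.099/41 = 0.002 SD. The pooled test is therefore free of this mechanism.

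**False-positive rate at an unadjusted 5%, r = 0.9 to 0.6**

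| True structure | Rank-sum on change, 13 v 28 | Signed-rank within the 13 |
|---|---|---|
| Continuous gradient | 16-57% | 13-41% |
| Clusters 2 SD apart | 10-33% | 7-23% |
| Clusters 3 SD apart | 7-17% | 6-12% |
| Clusters 4 SD or more apart | 5-9% | 5-7% |

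The pooled signed-rank test in all 41 stays at about 5% throughout. If separation is counted in SDs of the observed score instead, the 4 SD row is already at about 5%.

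**With Benjamini-Hochberg.** The number of taxa tested is not given. Assuming 50, the strictest first-rank threshold is 0.05/50 = 0.001. At that threshold the rank-sum rates for r = 0.6 / 0.9 are about 8% / 0.5% (gradient), 3% / 0.2% (2 SD) and 0.5% / 0.1% (3 SD). More taxa would make the threshold stricter. Genuine changes in other taxa would relax it and raise these rates.

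**The case against.** The strongest reply is that three links in the argument are inferred.

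1. **The label.** No assignment rule is written. Clustering on the whole genus profile, or an external classifier, would not be the same as taking the 13 highest on one score.
2. **The within-enterotype test.** SAP section 6 does not say that the signed-rank test is run by enterotype, and the matching outcome in Protocol 4.1 is for all 41.
3. **The between-enterotype test.** The rank-sum test is written for abundances, with no change score for taxa. Protocol 4.1 speaks of differing changes for BMI but only of a difference for the microbiota.

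All three observations are correct. What remains is that the Figure 1 legend, the stated purpose and the phrase about following the intervention in Protocol 4.1 all point to diet effects by enterotype. A label used at baseline and named after two genera is most naturally a baseline label built on those genera. Nothing in the plan rules the analysis out.

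A second reply is that the unadjusted rates are not those of the planned procedure. That also stands: Benjamini-Hochberg cuts them sharply. It deals with multiplicity, however, and leaves the estimated changes as biased as before.

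A third reply is that relative abundances are linked, so the remaining taxa cannot be treated as clean. This is accepted and is reflected in the fix.

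**Conclusion.** The concern holds as a conditional one. If the label comes from baseline Prevotella and Bacteroides, and change in those taxa is assessed by enterotype, this uncontrolled design cannot separate a diet effect from regression to the mean. The size is unknown. It ranges from substantial (a continuous gradient and a noisy single sample, before adjustment) to negligible (well-separated enterotypes), and it depends on the assumed reliability, separation and number of taxa.

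A reader might infer more than the documents support:

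- **That the plan prescribes biased tests.** It does not spell out by-enterotype change tests for taxa.
- **That the trial's error rate for these taxa is as high as 57%.** That figure is unadjusted, for the least favourable scenario examined in the table.
- **That the BMI findings are compromised.** The groups are not formed on BMI, so this mechanism does not reach the primary outcomes. Nor does it reach the pooled before/after tests.

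The problem is confined to a few taxa within a secondary outcome. It is worth correcting because the correction is cheap.

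**What to change.** In SAP section 6:

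- State which stool sample and which taxa assign enterotype, and by what rule.
- For those defining taxa (Bacteroides, Prevotella and their species), base any claim of a calorie-restriction effect on the pooled 41 only.
- Report their by-enterotype changes descriptively, without p-values and without claiming an enterotype-specific diet effect.
- Note that by-enterotype changes in other taxa may carry part of the same artefact, because the outcomes are relative abundances.

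The cost is a few sentences and no new data. The downsides are that no enterotype-specific diet effect can be claimed for the defining taxa, and that pooling may mask genuine shifts in opposite directions.
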